4.2.2.2 Restrictions on diet and lifestyle

No restrictions apply with regard to diet or lifestyle.

4.2.2.3 Restrictions regarding women of childbearing potential

Women of childbearing potential must be ready and able to use highly effective methods of birth control per ICH M3(R2) that result in a low failure rate of less than 1% per year when used consistently and correctly, and this during treatment within the trial and for at least one year after last dose of BI 836826 and 1 month after the last dose of ibrutinib (see [Section 3.3.2](#) and explanation given in the informed consent information form for more information on highly effective methods of birth control).

Male patients with partners of childbearing potential need to use condoms and ensure their partner is using an additional highly effective method of birth control, during the trial and until at least one year after the last dose of BI 836826 and 3 months after the last dose of ibrutinib.

5. VARIABLES AND THEIR ASSESSMENT

5.1 TRIAL ENDPOINTS

Primary endpoints:

- Recommended phase 2 dose of BI 836826 in combination with ibrutinib
- Number of patients with DLTs during the first treatment cycle

Secondary endpoint:

- MTD

5.1.1 Primary endpoint(s)

One primary endpoint is to determine the RP2D of BI 836826 in combination with ibrutinib. If a MTD can be determined based on the criteria as described in [Section 7](#), the RP2D will be either the MTD or a lower dose. The RP2D will be determined based on safety and efficacy criteria. Safety criteria include, but are not limited to the number of DLTs during the first treatment cycle, other AE and laboratory abnormalities may be considered in addition. Efficacy criteria include, but are not limited to the effect of BI 836826 on ALC, lymph node size as assessed by SPD, improvement of decreased blood cell counts related to CLL at baseline, overall response. Biomarkers may be considered in addition.

The second primary endpoint is the number of patients with DLT during the first treatment cycle. The number of evaluable patients per dose level with DLTs will be used to update the Bayesian model and to eventually determine the MTD.

5.1.2 Secondary endpoint(s)

The Secondary endpoint of this trial is the MTD.

The MTD may be considered reached if the probability that the true DLT rate is in the target interval [0.16, 0.33) is sufficiently large. For details on determination of MTD, please refer to [Section 7.1](#). For the definition of DLT, see [Section 5.3.6.2](#).

5.2 ASSESSMENT OF EFFICACY

5.2.1 Overall response assessment

Response will be assessed by the investigator according to modified IWCLL guidelines [[R10-4429](#)] (See [Appendix 10.2](#)) at all disease assessment timepoints specified in the flowchart. All relevant clinical and radiographic information required to make each assessment must be made available for source verification.

Imaging:

All relevant lymph node areas should be documented with either contrast enhanced Computerized Tomography (CT) (preferred) or contrast enhanced MRI at the time points indicated in the [Flow Chart](#).

The same method of assessment and the same technique (*e.g.*, scan type, patient position, dose of contrast, injection/scan interval) should be used to characterize each identified and reported lesion at baseline and during study treatment and follow up. If contraindication for contrast agents exists, non-contrast enhanced CT or MRI scans may be performed.

Disease/response status will be assessed with imaging (CT/MRI) at screening prior to the first dose of ibrutinib, and at the end of Cycles 3, 6, 9 and 12. In case patients qualify for prolonged treatment, CT/MRIs will be performed in addition at the end of cycles 16, 20 and 24. A CT/MRI scan will be performed at the EOT visit if it was not performed at a scheduled visit within 29 days prior to EOT ([R10-4429](#)). At the time of clinically suspected disease progression, a CT/MRI should be obtained; a confirmatory scan is not required in the case of PD.

The disease/response assessment will be based on Complete Blood Count (CBC) and imaging (CT or MRI). MRD assessments will coincide with the schedule of imaging studies. Physical examination of lymph nodes will be used to exclude PD prior to starting the next treatment cycle at visits where no imaging study is scheduled. Bone marrow biopsy results will be used to support the evaluation of CR, CRi and PR.

At all disease/response assessment timepoints, response to treatment (CR/CRi/PR/PR-L/SD/PD) should be determined based on the modified IWCLL criteria in [Appendix 10. 2](#).

The BOR is the best response recorded from the start of treatment until disease progression or initiation of subsequent therapy. Post-treatment assessments will be considered in the determination of best overall response as long as a patient does not initiate a new anti-CLL therapy.

5.2.2 CBC and differential

A CBC and differential should be obtained at each disease/response assessment timepoint in the same laboratory at the investigational site. The sample has to be obtained prior to administration of pre-medication and prior to the start of BI 836826, if an infusion is administered on the same day. Absolute lymphocyte count, neutrophil count, hemoglobin and platelet count have to be captured in the eCRF and will be considered for the disease/response assessment, (time points specified in the [Flow Chart](#)).

5.2.3 Bone marrow aspirate and biopsy

Bone marrow aspirate and biopsy for response assessment is mandatory according to IWCLL guidelines [[R10-4429](#)] in patients who meet all other IWCLL response criteria for CR. The bone marrow should be analysed morphologically and by flow cytometry and/or immunohistochemistry to check for CLL infiltration, or to evaluate a possible cause for persistent cytopenia.

Each time when a BM assessment is performed, a CBC with differential should be available, from the same day as the bone marrow biopsy.

A screening BM assessment is to be performed. Historical data from a BM is acceptable, if the BM assessment has been performed within 4 weeks of consent. A BM assessment will also be performed at EOT.

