⁵ Follow-up visits will no longer be required after approval of CTP Amendment 1. Follow-up for patients who terminate for any other reason at any time other than PD: Full response assessment at EOT or EoR;

⁶There will be an additional contact with regard to the End of Trial status as soon as the end of the whole trial is reached (see [Section 8.6](#)). Contact can be either a clinic visit or phone call. Visits will include vital status and anti-cancer treatment for CLL at the time of contact.

⁷Patients are **ONLY** required to be hospitalized overnight after the first 50% infusion of BI 836826 on Cycle 1 Day 2 if patient is at risk of TLS requiring monitoring and/or prophylactic treatments.

⁸Disease Assessment: Should be performed as close to the start date (within 7 days) of Ibrutinib during screening. Historical CT scans (up to 30 days prior to start of run-in phase) may be used at screening, if no other anti-CLL therapy (ies) have been given. Minimum of 7 days after BI 836826 administration (preferably between D 21 and D28 of Cycle 2 and 4); Subsequent 12 week Disease Assessments: >=21 days after BI 836826 administration and prior to start of next cycle (preferably between D21 and D28). Assessments to be performed every 12 weeks or 3 cycles from Cycle 1 Day 1 (C3, C6, C9, C12).

⁹Review of key laboratory values outlines in [Section 4.1.4](#) prior to first pre-dose administration of BI 836826

¹⁰After Informed Consent is obtained and review of inclusion/exclusion

¹¹In Cycle 1, done at Day 1, before start of BI 836826 infusion; Every 8 weeks during the treatment period, i.e. every other cycle (Cycle 2, 4, etc.) and EOT. PE to include weight. Height to be recorded at screening only.

¹²Vital signs (blood pressure, pulse rate and body temperature) will be recorded at every visit during screening, and treatment, before proceeding with any other protocol specific procedure and after at least 5 minutes of rest (See [Section 5.3.2](#) and [Section 6.1](#) for assessments)

¹³Single, resting 12 lead ECG to be performed at Screening, Day 1 of every Cycle and EOT, or whenever deemed necessary by the investigator (See [Section 5.3.4](#)).

¹⁴HBV DNA monitoring is only applicable to patients who are HBc antibody positive at screening (see [Section 5.3.3.4.1](#)). Patients who are HBc antibody positive at screening will be monitored for potential HBV reactivation by quantitative HBV DNA at visit 1 of every even course (Cycle 2, 4, 6, etc....) and at the EOT.

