3.3.2 Inclusion criteria

1. Diagnosis of CLL established according to IWCLL criteria ([R10-4429](#)) and documented within medical records.
2. Relapsed or refractory CLL pre-treated with at least one prior line of systemic therapy for CLL.
3. Indication for treatment consistent with IWCLL criteria, i.e. at least one of the following criteria should be met
 - a) Evidence of progressive marrow failure as manifested by the development of, or worsening of, anaemia and/or thrombocytopenia.

- b) Massive (i.e., lower edge of spleen ≥ 6 cm below the left costal margin) or progressive or symptomatic splenomegaly.
 - c) Massive nodes (i.e., ≥ 10 cm in longest diameter) or progressive or symptomatic lymphadenopathy.
 - d) Progressive lymphocytosis in the absence of infection, with an increase in blood ALC $\geq 50\%$ over a 2-month period, or a lymphocyte doubling time (LDT) of < 6 months (as long as initial ALC was $\geq 30000/\mu\text{L}$).
 - e) Autoimmune anaemia and/or thrombocytopenia that is poorly responsive to corticosteroids or other standard therapy.
 - f) Constitutional symptoms, defined as any one or more of the following disease-related symptoms or signs:
 - i. unintentional weight loss of 10% or more within the previous 6 months
 - ii. significant fatigue (i.e. ECOG PS 2 or worse; inability to work or perform usual activities)
 - iii. fevers higher than 100.5°F or 38.0°C for ≥ 2 weeks without other evidence of infection
 - iv. night sweats for > 1 month without evidence of infection
4. Clinically quantifiable disease burden defined as at least one of the following:
- a) either ALC $> 10\,000/\mu\text{L}$, or
 - b) measurable lymphadenopathy (at least one node > 1.5 cm in short diameter on CT or Magnetic Resonance Imaging (MRI) or
 - c) quantifiable bone marrow infiltration documented in a bone marrow biopsy during screening
5. Minimum interval to prior CLL treatment in line with the following requirements:
- a) Last dose of a cytotoxic drug, a monoclonal antibody targeting CD20, or an investigational drug to treat CLL at least 1 week prior to the first dose of ibrutinib.
 - b) Last dose of idelalisib at least 48 hours prior to the first dose of ibrutinib.
 - c) Last dose of alemtuzumab at least 4 weeks prior to the first dose of ibrutinib.

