6. INVESTIGATIONAL PLAN

6.1 VISIT SCHEDULE

The screening period is a maximum of 21 days prior to the start of the Run-In Phase. Patients who meet all trial eligibility criteria will continue into the Run-in phase and begin two weeks (+/- 2 days) of ibrutinib monotherapy dosing prior to the first infusion of BI 836826.

Treatment with BI 836826 will be administered in cycles of 28 days duration. The dose of BI 836826 will be tapered up to the target dose during Cycle 1 to mitigate the risk for IRRs and TLS. Treatment with BI 836826 starts with the first administration of 10 mg ('pre-dose') on Cycle 1 Day 1 (see [Section 3.1](#)), followed by 50% of the target dose of BI 836826 on Cycle 1 Day 2 and Cycle 1 Day 8. The first full dose of BI 836826 (100% of the target dose) will be administered on Cycle 1 Day 15.

In Cycles 2 to 4, patients will receive 100% of the target dose of BI 836826 on Day 1 and Day 15 of each cycle. In Cycles 5 to 12, BI 836826 will be administered at 100% of the target dose on Day 1 only. A response evaluation, including imaging (if clinically indicated), will be performed at the end of Cycle 3, 6, 9 (Day 21-28) and 12 (Day 21-30). Only those patients with CR, CRi, or MRD negative PR in the response assessment at the end of Cycle 12 will be allowed to continue with additional 12 Cycles of combination treatment or until relapse, undue toxicity, withdrawal of consent or until the end of the maximum treatment duration of BI 836826 at the end of 24 Cycles, whichever comes first. In patients who continue treatment beyond 12 cycles and proceed to Cycles 13-24, a response evaluation including imaging (if clinically indicated) will be performed at the end of Cycles 16, 20, and 24.

Once a patient stops the BI 836826 treatment, he/she will undergo an End of Treatment (EOT) visit.

In case the patient completes Cycle 12 or Cycle 24 and terminates treatment with BI 836826 according to protocol in the absence of PD, the assessments indicated for the EOT and End of REP (EoR) visit in the [flowchart](#) may be performed once at the time specified for the EoR visit.

In case a patient experiences PD, an EOT visit including imaging should be performed as soon as possible after discontinuation of BI 836826 and prior to initiation of subsequent therapy. An EoR visit should be performed 30 days (+ 7 days) after EOT.

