6.2.1 Screening and run-in period(s)

Screening Period:

The examinations required for the screening visit may be conducted within a time interval of 21 days prior to the start of ibrutinib and up to 35 days from the first drug administration of BI 836826 on Cycle 1 Day 1. Pre-ibrutinib disease assessments should be performed close to the start of ibrutinib (within 7 days). Patients who have consented should secure sourcing and be on a stable and continuous dosing of ibrutinib prior to Cycle 1 Day 1.

The site should call IRT after informed consent is obtained to register the patient as enrolled. The patient will be officially entered via IRT after all the eligibility criteria are met.

If for administrative or medical reasons, the patient does not start with study medication after the defined screening period, it is allowed to re-screen a patient within 7 days. In case a patient is re-screened, he/she will keep the same patient number and an unscheduled additional screening visit will be created with the examinations that were re-performed for screening.

Biomarkers tests, imaging and virology testing may not need to be repeated if performed within the permitted window, relative to Cycle 1 Day 1. Other tests (i.e. safety labs) must be performed if older than 48 hours.

Baseline Conditions:

Concomitant diagnoses present at study entry and/or during screening and relevant to the patient's safety during the trial as judged by the investigator will be recorded in the eCRF.

Demographics and Oncological History:

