Definitions of response and progression:

Complete Response (CR)

CR requires all of the following criteria to be met:

- Absolute lymphocyte count below $4 \times 10^9/L$.
- Regression of all target nodes/masses, i.e. all target lesions have a LD < 1.5 cm
- Disappearance/absence of all non-nodal non-target lesions, regression of all nodal nontarget lesions to normal sized lymph nodes
- Normal liver size (≤18 cm), based on CT imaging or non-palpable by Physical Exam
- Normal spleen size (≤12 cm), based on CT imaging or non-palpable by Physical Exam
- No evidence of new disease.
- Morphologically negative bone marrow, defined as normocellular marrow in relation to patient age, less than 30% of nucleated cells being lymphoid cells and no lymphoid nodules.
- Platelet count more than $100 \times 10^9/L$ (without exogenous growth factors or transfusion).
- Hemoglobin more than 110 g/L (without exogenous growth factors or transfusions)

- Absolute Neutrophil Count more than $1.5 \times 10^9/L$ (without exogenous growth factors).

Patients who fulfil all criteria for a CR (including a bone marrow examinations) but who have a persistent anaemia, thrombocytopenia, neutropenia or a hypocellular bone marrow related to prior or ongoing CLL therapy, but unrelated to CLL should be classified as CRi.

Partial Response (PR)

To define a PR, all of the following criteria must be met:

- No evidence of new disease
- At least one of the following laboratory criteria is present:
 - i. Platelet count higher than $100 \times 10^9/L$, or $\geq 50\%$ improvement over baseline (without exogenous growth factors or transfusion)
 - ii. Hemoglobin higher than 110 g/L, or $\geq 50\%$ improvement over baseline (without exogenous growth factors or transfusions)
 - iii. Absolute Neutrophil Count higher than $1.5 \times 10^9/L$, or $\geq 50\%$ improvement over baseline (without exogenous growth factors)
- Reduction in tumor load documented by at least two of the following criteria, with exceptions in the following situations where only 1 criterion needs to be met: (a) lymphadenopathy is the only disease manifestation (b) only lymphocytosis without lymphadenopathy is present at baseline, (c) a bone marrow assessment at screening shows quantifiable bone marrow infiltration as the only site of disease. In situation (a) only criterion (ii) will be applicable, in situation (b) only criterion (i), and in situation (c) only criterion (v).

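### A historical bone marrow can serve as the response baseline even when other CLL therapy followed it, so the marrow criterion for PR or PR-L can credit that therapy to the combination (minor)

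*Protocol*

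**What the plan says.** - **Historical marrow.** Protocol section 5.2.3 requires a screening marrow but allows a substitute: "Historical data from a BM is acceptable, if the BM assessment has been performed within 4 weeks of consent". No other condition is attached.
- **Historical CT.** Footnote 8 of the first flow chart accepts scans up to 30 days before run-in, but they "may be used at screening, if no other anti-CLL therapy (ies) have been given".
- **General timing.** Footnote 8 is attached to the whole disease-assessment block, which includes the marrow row. It says the assessment "Should be performed as close to the start date (within 7 days) of Ibrutinib during screening". Section 6.2.1 repeats the 7-day timing for pre-ibrutinib disease assessments.
- **Eligibility by marrow.** Inclusion 4c asks for "quantifiable bone marrow infiltration documented in a bone marrow biopsy during screening".
- **Prior therapy.** Inclusion 5a sets the gap before ibrutinib: "Last dose of a cytotoxic drug, a monoclonal antibody targeting CD20, or an investigational drug to treat CLL at least 1 week prior". Items 5b and 5c set 48 hours for idelalisib and 4 weeks for alemtuzumab.
- **Use in response.** In Appendix 10.2, a fall of at least 50% from baseline in marrow infiltration is PR criterion (v) and PR-L criterion (iv). PR normally needs two of five tumor-load criteria. Criterion (v) alone suffices where "a bone marrow assessment at screening shows quantifiable bone marrow infiltration as the only site of disease".
- **Baseline.** SAP section 6.7 takes the value closest to, but before, the first BI 836826 dose, unless specified otherwise.

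**The concern.** A response baseline should describe the disease when trial treatment starts. If CLL therapy is given after the baseline sample, a later fall mixes that therapy's effect with the combination's. The error runs one way: effective earlier therapy can only make the marrow response look larger. The protocol guards against this for CT and leaves it open for marrow.

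At stake is the PR or PR-L category of an affected patient. Section 5.1.1 names overall response among the efficacy inputs to the RP2D, and an MRD-negative PR is one of the response states that permits treatment after Cycle 12.

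**Working it through.** The plan gives no figure to reproduce. The check is date arithmetic followed by the Appendix 10.2 rule.

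**Inputs**
- Historical marrow: up to 28 days before consent (section 5.2.3).
- Screening: "within a time interval of 21 days prior to the start of ibrutinib" (section 6.2.1). I assume consent opens a single 21-day screening period, as the flow-chart days (-35 to -15) imply.
- Run-in: patients "begin two weeks (+/- 2 days) of ibrutinib monotherapy dosing" (section 6.1).
- Minimum gap before ibrutinib: 7 days (cytotoxic, CD20 antibody, investigational), 2 days (idelalisib), 28 days (alemtuzumab).

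**Oldest baseline if only section 5.2.3 is applied**
- Marrow to ibrutinib: 28 + 21 = 49 days.
- Marrow to Cycle 1 Day 1: 49 + 14 = 63 days (61 to 65 with the run-in window).

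**Room for therapy after the marrow = interval minus required gap**
- Cytotoxic, CD20 or investigational: 49 - 7 = 42 days.
- Idelalisib: 49 - 2 = 47 days.
- Alemtuzumab: 49 - 28 = 21 days.

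**Same calculation if the 7-day timing is enforced for marrow**
- Cytotoxic, CD20 or investigational: 7 - 7 = 0 days.
- Idelalisib: 7 - 2 = 5 days.
- Alemtuzumab: 7 - 28 is negative, so none.

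The 7-day timing alone nearly closes the gap. The CT condition, applied to marrow, closes it for every drug class.

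**Effect on the marrow criterion (assumed infiltration values)**
- Historical 80%, 40% after the earlier therapy, 40% on trial. Against the historical marrow: (80 - 40)/80 = 50%, criterion met. Against the marrow at trial start: (40 - 40)/40 = 0%, not met.
- Historical 80%, 45% after the earlier therapy, 40% on trial. Against the historical marrow: 50%, met. Against the marrow at trial start: (45 - 40)/45 = 11%, not met.

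**When this changes the category**
- Marrow the only site: the marrow criterion decides.
- Only nodes, or only lymphocytosis without nodes: Appendix 10.2 applies a different single criterion for PR, so marrow has no effect on PR.
- Otherwise, no other tumor-load criterion met: marrow alone is not enough, so no effect.
- Exactly one other criterion met: marrow supplies the second and can turn SD into PR or PR-L.
- Two or more others met: the tumor-load requirement is satisfied without marrow, so no effect.

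In every case PR and PR-L also require a blood-count criterion, no new disease and no progression.

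**The case against.** The strongest reply is that other text already limits the problem. Inclusion 4c calls for a biopsy in the screening period, PR exception (c) refers to a screening marrow, and footnote 8 and section 6.2.1 ask for assessment within 7 days of ibrutinib. Much of this stands. A reader might infer an open licence for 42 to 47 days of intervening therapy; the documents support that only as an outer bound. Equally, the 7-day timing is worded as a recommendation and section 5.2.3 expressly lets historical data stand in for the screening marrow, so the conflict is unresolved.

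Three further inferences are tempting and not supported:
- **That response is inflated generally.** Section 5.2.1 bases response on blood counts and imaging, with marrow in support. CR uses an absolute marrow standard. Scheduled marrow is at screening and EOT only; others follow suspected CR or MRD-negative blood.
- **That patients would wrongly continue after Cycle 12.** Continuation requires CR, CRi or an MRD-negative PR, and MRD negativity is an absolute threshold (section 5.2.6). A marrow artefact in an MRD-positive patient opens nothing.
- **That patients without current disease enter under 4c.** The wording of 4c points to a screening biopsy, and inclusions 2 and 3 require relapsed or refractory disease with a current indication for treatment. These make the case less likely without excluding it.

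Two limits on this review also stand. The public SAP omits text between sections 5.2.2 and 6, so a response-specific baseline rule there cannot be ruled out. And section 2.1 stops recruitment, so a change to a screening rule governs no new patient.

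**Conclusion.** The gap is real and minor. As written, section 5.2.3 can supply a baseline marrow that predates other CLL therapy, by at most 49 days before ibrutinib, and nothing visible in either document excludes this. PR criterion (v) or PR-L criterion (iv) can then credit that therapy to the combination. The consequence is confined to marrow-only disease and to patients with exactly one other tumor-load criterion met. The documents give no basis for saying how many patients that is.

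DLT counts, MTD, CR and MRD status are untouched. Response is neither a primary nor a secondary endpoint, and marrow is not itself listed among the RP2D inputs, so the effect on the RP2D judgement and on continuation after Cycle 12 is small.

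The conclusion assumes consent at the start of one screening period, no newer marrow before BI 836826, and no contrary baseline rule in the unseen SAP text. The infiltration values are illustrative.

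**What to change.** 1. Reconcile section 5.2.3, footnote 8 and inclusion 4c on when the baseline marrow may be taken and whether a historical one satisfies 4c.
2. State that a historical marrow is a valid response baseline only if no anti-CLL therapy was given between it and the first ibrutinib dose, as footnote 8 does for CT.
3. Because recruitment is stopped, apply this mainly in the analysis. For each enrolled patient with a historical marrow, compare its date with the last dose of prior therapy. Section 6.2.1 lets therapy dates be month and year only, which may not settle the order. Use source records then; section 8.3.1 requires documented evidence that inclusion 5 was met.
4. Where therapy intervened, treat PR criterion (v) and PR-L criterion (iv) as not assessable.
5. State that a marrow-only patient so affected is non-evaluable for PR and PR-L. Appendix 10.2 leaves no other route to PR for such a patient, and its non-evaluable category covers only imaging problems.

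The cost is a few lines of text and a date check, with no extra biopsy. The downside is that a few patients may lose marrow-based response evaluability.
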